10.6 Photographic Cosmetic Assessment

An important outcome of this study is the cosmetic outcome of hypofractionated radiation versus conventional radiation and the risks of late radiation morbidity. These side effects include telangiectasia, breast fibrosis, scar retraction and skin pigmentation changes, which may all affect the cosmetic result. As this is not a blinded study, cosmetic assessment will be by digital photography reviewed by a Central Adjudication Committee unaware of treatment allocation evaluating late radiation morbidity.

Confidential bilateral digital photographs (excluding the face) will be taken with a digital camera:

- 1) Standing, anterior photo to show both breasts with the arms at 45° from the body and
- 2) Close up of treated area to show the surgical scar and surrounding reconstructed tissue at 24 months post radiation.

Photographs will be captured of both breast/reconstructed chest walls at the following time points:

- Before radiation, only for patients with immediate reconstruction
- 24 months after the completion of radiation for all patients.

Photographs of both breasts will be collected as above and reviewed by a blinded Central Adjudication Committee according to the modified EORTC Cosmetic Rating System. Study participants will be identified only by study ID number of their photographs to ensure confidentiality. De-identified photographs will be submitted to IROC Rhode Island where they will be prepared for review and archived with the patient record. See section 6.3 for instructions for submission of photographs. The review process has been used extensively in the past, including in the recent Canadian RAPID study of partial breast radiation. The treated breast will be compared to the intact opposite breast or contralateral reconstructed chest wall. For patients who have their final reconstruction performed prior to starting radiation, there will also be pre-radiation photographs taken. Patients who develop an ipsilateral breast cancer or lymph node recurrence before the 24 month photography assessment will not be assessed. We will use the modified EORTC digital photographic method used in the Canadian RAPID trial. This approach has been shown to be reliable in intact breast patients and is validated in detecting the effects of radiation morbidity. [45-47]. Unfortunately, there are no validated photographic assessment tools in reconstructed breast patients.

The confidential photographs will be assembled into presentation format to allow for efficient review by the Central Adjudication panel. The online training module will be reviewed and utilized by the panel. Two panels of 3 multidisciplinary experts will form the Central Adjudication panel, including representatives from the disciplines of radiation oncology, breast surgery and plastic surgery. Once all photographs are collected there will be a minimum of 1-2 in-person meetings by panels to review and score the photographs. This method has been used extensively in the past, including the recent NSABP B-39 trial and the Canadian RAPID partial breast trial, and found to be valid and reliable. The Central Adjudication panel includes members with significant experience in conducting photographic cosmetic assessment in prior studies.

10.7 Health Economic Analysis

A reduction in number of radiation treatments and thereby number of visits to the radiation therapy department will benefit patients directly, both in terms of reduced direct and indirect healthcare costs. Direct healthcare costs are expected to go down because of an expected reduction in health care utilizations services (e.g., office visits, emergency room visits, inpatient admissions). With short-course treatment patients may be able to take less time off from work and/or return to work faster. Potential improvements in cosmetic-outcomes and side effects of radiation therapy with short-course therapy could also translate into a reduction in utilization of health care services, further enhancing the economic impact of hypofractionation. Indirect costs are also expected to be lower for the intervention arm because patients in this arm are expected to resume normal activities sooner. This in turn would help save family caregiver time as well as the cost of dependent care, which will further add to the saving in indirect costs. Therefore, robust measurement of the patient resources used to receive radiation therapy and utilization of health services is a critical component of this randomized multicenter international trial.

To assess patient resources used for receipt of radiation therapy and recovery, patients will be asked to complete the Health Care Expense Questionnaire which will take about 20 minutes. They will be given a **Health Care Expense Diary and Questionnaire booklet** (Appendix VII) with question domains to be filled out during radiation therapy and up to 8 weeks after radiation in order to help improve recall for completion of this questionnaire. They will use information recorded in the Health Care Expense Diary to complete and submit the Health Care Expense Questionnaire at the 2-8 week clinic visit.

Upon completion of radiation therapy patients will be given the **Health Care Utilization Diary** (Appendix VIII) to record any clinic visits, visits to emergency rooms, to physical therapists, and/or any other health care services used, as well as any hospital admissions that occur in the year that following radiation therapy. At the 12-month post-radiation visit, patients will be asked to report the utilization of health care resources in the interval between radiation completion and the end of 12-month follow-up using the completed Health Care Utilization Diary.

Treating institutions in the U.S. are also instructed to submit CPT code charges generated from the time of registration to 12 months after the completion of radiation therapy. These will be used to estimate a standardized direct cost of care.

Questions are adapted from the Medical Expenditure Panel Survey-Household Component (MEPS-HC) created by AHRQ [REDACTED]. The questionnaire can be found in [Appendix VII](#).

11.0 END OF TREATMENT/INTERVENTION

11.1 Duration of Treatment

Radiation therapy is to be given 5 days a week for 5-6 weeks in Arm 1 and 5 days a week for 3-4 weeks in Arm 2, per [Section 7.4](#).

11.2 Criteria for discontinuation of protocol treatment

Radiation treatment will continue unless one of the following criteria applies:

- Disease progression or relapse
- General or specific changes in the patient's condition render the patient unacceptable for further treatment in the judgment of the treating physician
- Patient withdrawal or non-compliance
- Patient receives alternative treatment (non protocol treatment that replaces standard RT or RT not per protocol) before or during protocol treatment period
- Patient experiences reconstruction related complications to the ipsilateral breast prior to start of radiation. No further follow up will be required for these patients (see Section 11.4.2).

11.3 Follow-up

11.3.1 Duration of follow up

Patients who complete radiation therapy and breast reconstruction-will be followed as outlined in Section 5.0 until disease recurrence, contralateral breast cancer, or a non-breast second primary cancer; or until an alternative treatment is given for up to 15 years after the end of radiation therapy. All follow up (including survival) done after 5 years will be gathered by record review only.

11.3.2 Follow up for patients who do not complete radiation and breast reconstruction

Patients who complete radiation per protocol, but who do not complete reconstruction will also be followed as outlined in [Section 5.0](#) until disease recurrence, contralateral breast cancer, or a non-breast second primary cancer; or until an alternative treatment is given for up to 15 years

after the end of radiation therapy. All follow up (including survival) done after 5 years will be gathered by record review only.

Patients who experience disease recurrence, contralateral breast cancer, or a non-breast second primary cancer, or alternative treatment will discontinue protocol therapy and no further follow up will be required.

11.4 Managing Ineligible Patients and Registered Patients Who Never Receive Protocol Intervention

11.4.1 Ineligible patients

Definition of ineligible patient: A study participant who is registered to the trial but does not meet all of the eligibility criteria is deemed to be ineligible.

Follow-up for ineligible patients who continue with protocol treatment: Patients who are deemed ineligible after registering may continue protocol treatment, provided the treating physician, study chair, and executive officer agree there are no safety concerns if the patient continues protocol treatment. All scans, tests, and data submission are to continue as if the patient were eligible. Notification of the local IRB may be necessary per local IRB policies.

Follow-up for ineligible patients who discontinue protocol treatment: For patients who are deemed ineligible after registering to the trial, who start treatment, but then discontinue study treatment, the same data submission requirements are to be followed as for those patients who are eligible and who discontinue study treatment.

11.4.2 Follow-up for patients who are registered, but who never start study treatment:

For all study participants who are registered to the trial but who never receive study intervention* (regardless of eligibility), the follow-up requirements are specified below.

- Baseline, off treatment, and end of study form required. See the Data Submission Schedule accompanying the All Forms Packet.
- * Patients who experience reconstruction related complications before the start of radiation will not receive protocol treatment, and the end of study form will be completed for these patients.

11.4.3 Follow-up for patients who are registered, but withdraw after starting study treatment

- Document the reason(s) for discontinuation of therapy on data forms.
- Follow the patient for protocol endpoints as required by the Study Calendar until disease recurrence, contralateral breast cancer, or a non-breast second primary cancer or alternative treatment.

11.5 Extraordinary Medical Circumstances

If at any time the constraints of this protocol are detrimental to the patient's health, protocol therapy shall be discontinued. In this event:

- Document the reason(s) for discontinuation of therapy on data forms.
- Follow the patient for protocol endpoints as required by the Study Calendar until disease recurrence, contralateral breast cancer, or a non-breast second primary cancer or alternative treatment.

12.0 STATISTICAL CONSIDERATIONS

12.1 Study Design

This is a randomized, two-arm, un-blinded, non-inferiority trial comparing the impact of hypofractionated dosing (vs. standard dosing) of radiation on the 24-month breast reconstruction complication rate.

12.2 Sample Size, Accrual Time and Study Duration

Our target sample size will be 792 evaluable patients (396 in each arm). To account for 10% drop-out due to cancellations or protocol deviations, our target accrual is 880 patients (440 per arm) (90% of 880 is 792).

The study design is a randomized, un-blinded, non-inferiority trial. It is assumed that the two-year breast reconstruction complication rate for the control arm (Arm 1: standard fractions) is 25%. Other assumptions for the sample size determination include:

- α (one-sided) = 0.025
- power = 90%
- non-inferiority margin: the absolute increase in the proportion of patients who experience
- a breast reconstruction complication within two-years is 10% above that of the control arm.
- one interim analysis (when 30% of the information is obtained) for futility

Under an alternative hypothesis that the true rates in the two arms are equal, a sample size of 792 (396 per arm) evaluable patients would give us 90% power to reject the null hypothesis of inferiority. The final analysis will take place after all patients have reached two years post-radiation. The anticipated accrual period is approximately 30 months, and the total study duration is approximately 60 months. We anticipate being able to accrue approximately 30 patients per month based on our best estimate extrapolated from recently closed intact breast trials looking at similar fractionations. It should be noted that if we instead assumed a complication rate of 50% in the control arm (the most statistically conservative, in terms of sample size), the above sample size would still give us approximately 80% power to reject the null hypothesis of inferiority (again with one-sided α of 0.025).

12.3 Statement of Primary Endpoint

12.3.1 Primary Endpoint

Our primary endpoint is the rate of breast reconstruction complications, defined in Section 10.1.

Routine revisions, such as dog-ear corrections, fat grafting, and contralateral breast revision will be recorded, but not counted towards primary endpoint events.

12.3.2 Analysis Plan for Primary Endpoint

The null hypothesis for our primary analysis is that the proportion of patients who experience a breast reconstruction complication within two years after the end of radiation treatment on Arm 2 (hypofractionated dosing) (denoted π_2) will be at least 0.1 higher than the proportion of patients in Arm 1 (denoted π_1) (standard dosing) (i.e. that hypofractionated dosing is inferior to standard dosing). This will be tested using a two-sample test of proportions. In particular, we will calculate the test statistic: $Z = (\pi_1 - \pi_2 + 0.1) / [\pi_1(1 - \pi_1)/n_1 + \pi_2(1 - \pi_2)/n_2]^{1/2}$, where n_1 and n_2 are the numbers of patients in Arms 1 and 2, respectively.

Interim analysis decision rule

Interim analysis of inferiority of hypofractionated PMRT (futility) as compared to conventional PMRT will be conducted when 30% of patients are enrolled and have reached two years post-radiation. The Lan-DeMets family of alpha and beta spending functions corresponding to the O'Brien-Fleming boundary are used for controlling overall type II error rates. Inferiority of the hypofractionated PMRT will be concluded if $p\text{-value} > 0.843$ (corresponding to $Z < -1.007$). The second stage of this clinical trial shall continue if $p\text{-value} \leq 0.843$.

Final analysis decision rule

Final analysis will be conducted when all target patients are enrolled and have reached 2 years post radiation. Non-inferiority of hypofractionated PMRT will be concluded if $p\text{-value} < .025$ (corresponding to $Z > 1.96$) and inferiority of hypofractionated PMRT will be concluded if $p\text{-value} \geq .025$ (corresponding to $Z \leq 1.96$).

Study Operating characteristics

Simulation studies of 10,000 clinical trials are conducted for the proposed group sequential design. The probabilities of early stopping (at the interim analysis) and empirical powers for various scenarios are summarized in the following table. Of particular interest, assuming that the two-year breast reconstruction complication rate is 25% for the control arm (Arm 1: conventional PMRT) and 35% for the hypofractionated PMRT (Arm 2), where the Arm 2 treatment is inferior to Arm 1, there is a 14.45% chance of stopping the trial early to conclude that hypofractionated PMRT is inferior. In another scenario where the complication rate of the conventional PMRT is 25% and that of hypofractionated is 25%, where the Arm 2 treatment is truly non-inferior to Arm 1, the likelihood of stopping early to conclude inferiority is 0.24% and the likelihood of the trial concluding that hypofractionated PMRT is non-inferior to conventional one is 90.84% (power).

Reconstruction complication rate		Interim analysis conclusion		Early stopping	Final analysis conclusion		Rejection (of H_0) rate
Conventional	Hypofractionated	Noninferior	Inferior		Noninferior	Inferior	
25%	35%	0.00%	14.45%	14.45%	2.37%	83.18%	2.37%
	30%	0.00%	2.86%	2.86%	34.51%	62.63%	34.51%
	25%	0.00%	0.24%	0.24%	90.84%	8.92%	90.84%

It should be noted that the primary analyses will be an intent-to-treat analysis where all patients randomized will be included in the analysis and will be analyzed based on the arm they were randomized to regardless of actual radiation schedule received. This analysis will not be stratified. Due to the random treatment assignment with stratification for the timing of reconstruction and type of reconstruction, it is expected that the baseline patient characteristics, including the planned reconstruction procedures, are roughly balanced across the two treatment arms. A sensitivity analysis stratified by timing and type of reconstruction surgery will be conducted.

The frequency and the proportion of patients who enrolled in the trial prior to reconstruction surgery who did not receive the surgery within 18 months of radiation as specified in the eligibility criteria will be summarized separately by arm. A secondary analysis excluding these patients will be conducted.

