- b) Rib fracture (rare) (Grade 1-3)

9.2.3 Non CTCAE Reconstruction Associated Complications:

The primary endpoint of this trial is the reconstruction complication rate at 24 months after radiation that requires hospitalization or re-operation. (Complications related to the contralateral breast will be collected but will not count towards the assessment of the primary endpoint, ipsilateral breast complications will be counted towards the primary endpoint). This is an adverse event rate not well characterized by the CTCAE terminology, and therefore will be recorded separately from CTCAE toxicity as follows:

- a. Capsular contracture (Baker grades III-IV would only count towards the primary endpoint)
Definition of Capsular contracture grades (to be captured in Rave)
 - Grade I — the breast is normally soft and appears natural in size and shape
 - Grade II — the breast is a little firm, but appears normal
 - Grade III — the breast is firm and appears abnormal
 - Grade IV — the breast is hard, painful to the touch, and appears abnormal
- b. Complete failure of the implant/skin flap
- c. Unplanned admission for reconstruction related issue(s) including but not limited to infection, wound healing complication or pain
- d. Unplanned return to the operating room for reconstruction related issue including but not limited to infection, prosthesis exposure, failed reconstruction, implant removal, wound healing complications or contracture management

Routine revisions, such as dog-ear corrections, fat grafting and revising the contralateral breast will not be scored as an adverse reconstruction event. Additionally, a contracture that is corrected when the tissue expander is exchanged for an implant or autologous tissue flap will not be scored as an event.

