12.7.2 Adverse Event Stopping Rule

Throughout the course of the study, we will monitor adverse events in both study arms, and may suspend accrual if patients are experiencing a large number of adverse events. In particular, we will temporarily suspend accrual if at any time observed events considered at least possibly related to study treatment (i.e., an adverse event with attribute specified as possible, probable, or definite) meet the following criteria:

- If 25 or more of the first 50 treated patients (or 50% of all patients after 50 patients have been accrued) experience a grade 3 or higher CTCAE adverse event (with the exception of acute dermatitis).

- If 5 or more of the first 50 treated patients (or 10% of all patients after 50 patients have been accrued) experience a grade 4 or higher CTCAE adverse event.

It should be noted that, if unexpected adverse event profiles are observed which do not meet any of the above criteria, but are nevertheless worrisome, we may still consider temporarily suspending accrual. Also, adverse event stopping rules may be modified if during the course of the study, new information becomes available which suggests that such a modification is necessary, or if, after temporarily stopping accrual, the above rules are found to be overly conservative.

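### At the planned accrual rate the futility look comes after enrolment has closed, and the only numerical rule active during accrual pools the arms and does not count most reconstruction complications as such

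*Combined protocol and SAP*

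**What the plan says.** **Interim look.** Section 12.3.2 plans a single futility analysis of the primary endpoint. It "will be conducted when 30% of patients are enrolled and have reached two years post-radiation" and concludes inferiority if Z < -1.007 (p > 0.843). The operating-characteristics table gives a 14.45% chance of stopping early when the true rates are 25% and 35%.

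**Accrual.** Section 12.2 states "Our target sample size will be 792 evaluable patients (396 in each arm"), inflated to 880 for 10% drop-out, at about 30 patients a month. "The anticipated accrual period is approximately 30 months", and total study duration is about 60 months.

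**Adverse-event rule.** Section 12.7.2 suspends accrual temporarily on CTCAE events at least possibly related to treatment. The grade 3+ criterion, which excepts acute dermatitis, reads: "If 25 or more of the first 50 treated patients (or 50% of all patients after 50 patients have been accrued"). The grade 4+ criterion is 5 of the first 50, then 10% of all patients. Events are monitored in both arms, but neither criterion has a per-arm count or a between-arm comparison. The section also allows accrual to be suspended for other worrying, unexpected adverse-event profiles, without a threshold.

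**Where the primary-endpoint events are recorded.** Section 9.2.3 says of the reconstruction complication rate: "This is an adverse event rate not well characterized by the CTCAE terminology, and therefore will be recorded separately from CTCAE toxicity". Section 9.4.1 also keeps grade 4 wound healing that needs a major flap reconstruction out of the CTCAE record. Section 9.2.1, however, lists wound infection, wound complication and wound dehiscence as solicited CTCAE terms.

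**DSMB.** Section 12.7.1 provides six-monthly reports of efficacy, adverse-event and administrative information, with no decision threshold.

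**The concern.** Section 1.1 names adverse events, especially with breast reconstruction, as the key question, and Section 1.0 says hypofractionation has not been studied in that setting. One would therefore expect a quantitative check, by arm, on reconstruction complications while patients are still being randomised. The plan's one formal look at that endpoint waits for two years of follow-up on 30% of patients. The rule that operates earlier uses a different classification of events and a denominator that mixes the arms. If hypofractionation caused more contractures, reconstruction failures or re-operations, a large excess could build up throughout enrolment without crossing any stated numerical limit.

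**Working it through.** **1. The design figures reproduce.** Inputs from 12.2: one-sided alpha 0.025, power 90%, control rate 25%, margin 10 points. The standard non-inferiority formula for two proportions gives 395 per arm, 790 in total (stated 792), and 792/0.9 = 880. The upper tail beyond Z = -1.007 is 0.843, as stated. A simulation with 119 per arm at the look and 396 at the end gives early stopping of 16.0%, 3.2% and 0.28% at hypofractionated rates of 35%, 30% and 25% (stated 14.45%, 2.86%, 0.24%) and power of 90.1% (stated 90.84%). The disagreement is not with these figures.

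**2. Calendar time of the look.**
- Accrual ends at 880/30 = 29.3 months (stated: about 30).
- Time of look = 0.30 × N/30 + lag + 24 months, where lag is the time from registration to the end of radiation.
- N = 792: 237.6/30 + 24 = 31.9 months with no lag; 32.7 to 33.3 with radiation time of 16 treatment days (0.74 month) to 6 weeks (1.38 months).
- N = 880: 264/30 + 24 = 32.8 months with no lag; 33.5 to 34.2 with radiation time.
- The documents give no registration-to-radiation interval. An assumed total lag of 3.5 months gives 35.4 to 36.3 months.

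The look therefore falls 2.6 to 4.8 months after the last enrolment when the lag is at most radiation time, and later with any wait.

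**3. Accrual rate at which this changes.** Setting the two times equal gives rate = (880 − 0.30 N)/(24 + lag). With radiation time only, this is 24.3 to 26.0 a month; over lags of 0 to 3.5 months it is 22.4 to 26.8. At 20 a month, with radiation time, the look comes at month 36.6 to 38.6. By then 732 to 772 patients are enrolled and 108 to 148 are not.

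**4. Dilution in the pooled rule.** With equal allocation the pooled rate is the mean of the two arm rates. If 20% of control patients have a grade 3+ event, the hypofractionated arm needs 80% to reach 50% pooled. For the first 50 patients, assume 25 per arm and grade 3+ rates of 15% (control) and 60% (hypofractionated). These rates are illustrative and not from the documents.
- Pooled trigger: P[Bin(25, 0.15) + Bin(25, 0.60) ≥ 25] = 0.029.
- Same percentage within the hypofractionated arm: P[Bin(25, 0.60) ≥ 13] = 0.846.

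**5. If every reconstruction complication did count.** With control at the planned 25%, the pooled 25-of-50 trigger would fire with these probabilities:

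| Hypofractionated rate | P(25 or more of 50) |
|---|---|
| 35% | 0.2% |
| 50% | 4% |
| 60% | 16% |
| 75% | 57% |

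Bringing these events into the existing rule, without splitting it by arm, would not close the gap.

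**6. False alarms if the thresholds are split by arm.** Equal true rates in both arms, 25 patients each:

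| Criterion | Assumed true rate | Either arm (13 or 3 of 25) | Pooled (25 or 5 of 50) |
|---|---|---|---|
| Grade 3+ | 20% | below 0.1% | below 0.1% |
| Grade 3+ | 40% | 28% | 10% |
| Grade 4+ | 1% | 0.4% | below 0.1% |
| Grade 4+ | 2% | 2.6% | 0.3% |
| Grade 4+ | 5% | 24% | 10% |

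**The case against.** - **A reader might infer that reconstruction complications are left out of the adverse-event rule altogether.** The documents do not support that. Grade 3+ wound infection, wound complication and wound dehiscence are solicited CTCAE terms, and Section 9.3 says attribution covers radiation and reconstruction. Such events can enter 12.7.2 when judged at least possibly related. What stays outside is contracture, implant or flap failure, and unplanned admission or re-operation as such.
- **A reader might infer that nothing could stop accrual for this harm.** The clause on worrying adverse-event profiles and the six-monthly DSMB reports could each lead to a suspension, and Section 9.2.3 itself calls the complication rate an adverse event rate. Both mechanisms stand, but they are judgement without a threshold.
- **A reader might infer that the interim look can never spare a patient enrolment.** That holds only near the planned rate, which 12.2 calls a best estimate extrapolated from other trials. The look is also labelled futility, not safety, and could report inferiority about two years before the planned end at month 60.
- **Moving the look to 12-month status is tempting.** Sections 3.2.12 and 7.2 allow reconstruction up to 18 months after radiation, and Section 4.6 classes expander patients as delayed. At 12 months some delayed patients could not yet have several of the component events, so 12-month status is a different endpoint by timing stratum. The plan gives neither a 12-month control rate nor a 12-month margin.
- **Per-arm thresholds raise the false-alarm rate.** This is true where events are common (step 6), so the counts need checking before adoption.

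**Conclusion.** The concern holds in limited form. On the plan's own accrual figures the futility look falls about 3 to 5 months after enrolment closes, so it cannot limit enrolment unless accrual drops below about 24 to 26 a month, a shortfall of roughly 15 to 20%. During accrual no numerical by-arm threshold exists for the complications that make up the primary endpoint, and the one numerical rule is insensitive to an excess in one arm (3% v 85% in the illustration). The timing result rests on steady accrual of 30 a month and on radiation time as the minimum lag; a longer wait strengthens it. The dilution result rests on assumed event rates and 25 patients per arm. The validity of the 24-month non-inferiority analysis is not in question. This is a gap in protection during accrual that should be closed because closing it is cheap.

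**What to change.** 1. In 12.7.2, apply the grade 3+ and grade 4+ thresholds within each arm as well as overall, and state the false-alarm rates. The grade 4+ count in small samples may need recalibrating: at an assumed 5% rate in both arms, 3 of 25 in either arm fires 24% of the time against 10% pooled.
2. In 12.7.1, add Section 10.1 complications by arm to the six-monthly DSMB report. Attach a non-binding, one-sided harm boundary on time to first complication (for example Haybittle-Peto, p < 0.005) that prompts temporary suspension of accrual for DSMB review, and show its operating characteristics.
3. In 12.3.2, keep the 24-month futility look and the final analysis, and state that at planned accrual the look does not limit enrolment. Do not replace it with a 12-month look.

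**Cost.** Protocol wording, one set of operating characteristics and one by-arm DSMB table. The trial is un-blinded and the study calendar already collects reconstruction complications at clinic visits from before radiation to five years, so no new data are needed. A non-binding harm boundary adds no type I error to the non-inferiority claim. The downside is a few more temporary suspensions.

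### The final decision rule in section 12.3.2 concludes inferiority whenever non-inferiority is not shown, leaving no 'not demonstrated' outcome

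*Combined protocol and SAP*

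**What the plan says.** Section 12.3.2 (Analysis Plan for Primary Endpoint) takes as its null that the two-year complication proportion in Arm 2 exceeds that in Arm 1 by 0.1 or more, and glosses this null as inferiority of hypofractionation. The statistic is the difference π1 - π2 plus 0.1, divided by its unpooled standard error, so large positive values favour non-inferiority.

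- **Final rule.** Non-inferiority is concluded if p < .025 (Z > 1.96), "and inferiority of hypofractionated PMRT will be concluded if" p is .025 or more (Z at or below 1.96). No third outcome is given.
- **Interim rule.** At 30% of patients: "Inferiority of the hypofractionated PMRT will be concluded if" p > 0.843 (Z < -1.007); otherwise the trial continues. Sections 12.2 and 12.3.2 both describe this look as one for futility.
- **Operating characteristics.** The table places every final non-rejection in an 'Inferior' column under the heading 'Final analysis conclusion'. The text applies the same language to equal arms: "where the Arm 2 treatment is truly non-inferior to Arm 1, the likelihood of stopping early to conclude inferiority is 0.24" per cent.

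**The concern.** A one-sided p of .025 or more says only that an excess of 10 points has not been ruled out. It does not say that such an excess exists. The written rule joins two different situations, a result that points to an excess above the margin and a result too imprecise to tell, and gives both the same positive conclusion. Section 12.3.2 specifies no confidence interval for the difference, so this two-way verdict is the planned primary result. At stake is the stated conclusion of a phase III trial meant to inform practice: a schedule that meets the plan's own definition of non-inferior could be concluded inferior because the estimate was imprecise.

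**Working it through.** **Inputs (section 12.2).** "α (one-sided) = 0.025"; control "rate for the control arm (Arm 1: standard fractions) is 25" per cent; margin: "a breast reconstruction complication within two-years is 10% above that of the control arm"; "Our target sample size will be 792 evaluable patients (396 in each arm"). Section 12.3.2 supplies the final cut-off of 1.96, the interim cut-off of -1.007 at 30% information, and the unpooled Z.

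**1. Reproduce the design.** The fixed-sample formula with 25% in both arms, margin 0.10, one-sided alpha 0.025 and 90% power gives 395 per arm (stated 396). 792/0.90 = 880, as stated. At 396 per arm with equal rates, SE = √(2 × 0.25 × 0.75/396) = 0.0308 and power = Φ(0.10/0.0308 - 1.96) = 90.1%.

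**2. Reproduce the table.** I applied the two-stage rule using a bivariate normal with correlation √0.30.

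| True rates | Non-inferior: plan / check | Early stop: plan / check | Final 'Inferior': plan / check | Total concluded inferior: plan / check |
|---|---|---|---|---|
| 25% v 25% | 90.84 / 90.1% | 0.24 / 0.3% | 8.92 / 9.7% | 9.16 / 9.9% |
| 25% v 30% | 34.51 / 35.0% | 2.86 / 3.1% | 62.63 / 61.9% | 65.49 / 65.0% |
| 25% v 35% | 2.37 / 2.5% | 14.45 / 15.7% | 83.18 / 81.8% | 97.63 / 97.5% |

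The plan's totals are row sums: 0.24 + 8.92 = 9.16, 2.86 + 62.63 = 65.49 and 14.45 + 83.18 = 97.63. A binomial simulation of 400,000 trials gave totals of 10.0% and 64.9% for the first two rows. The early-stop gap in the third row (15.7% against 14.45%) does not bear on this point.

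The first two rows are non-inferior by the plan's definition, since the true excess is below 10 points. At a true rate of 27.5% the same calculation gives 33.1% concluded inferior.

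**3. One observed result.** Take 25% v 29% at 396 per arm.

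- SE = √[(0.25 × 0.75 + 0.29 × 0.71)/396] = √(0.3934/396) = 0.0315.
- Z = (0.25 - 0.29 + 0.10)/0.0315 = 1.90, below 1.96, so inferiority is concluded.
- 95% CI for Arm 2 minus Arm 1 = 0.04 ± 1.96 × 0.0315 = -2.2 to +10.2 points.

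In whole counts, 99 v 115 events (25.0% v 29.04%) gives Z = 1.89 and a CI of -2.1 to +10.2. With one event fewer, 99 v 114, SE = √[(0.1875 + 0.2050)/396] = 0.03148 and Z = (0.10 - 0.03788)/0.03148 = 1.97, and the trial concludes non-inferiority. One patient moves the verdict from non-inferior to inferior, with nothing between.

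**4. The interim boundary.** One-sided P(Z < -1.007) at the margin is 0.157. Assume about 119 per arm (30% of 396 = 118.8) and an observed control rate of 25%. Z = -1.007 then needs an Arm 2 rate of about 41.05%: SE = √[(0.1875 + 0.2420)/119] = 0.0601, and (0.25 - 0.4105 + 0.10)/0.0601 = -1.007. The observed excess is about 16 points, with 95% CI 16.05 ± 1.96 × 6.01, or about 4.3 to 27.8. The interval excludes 0 but not 10.

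**5. Sensitivity to the number analysed.** Section 12.3.2 says all randomised patients enter the primary analysis, and section 12.2 says: "To account for 10% drop-out due to cancellations or protocol deviations, our target accrual is 880 patients". With 440 per arm and no interim look, the chance of showing non-inferiority is 92.9% at 25% v 25% and 38.3% at 25% v 30%, so 7.1% and 61.7% would be concluded inferior. The picture is unchanged.

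**The case against.** The strongest defence is that 'inferiority' is only the plan's name for its null: section 12.2 speaks of rejecting the null of inferiority, and the table has a separate column for the rate of rejecting H0. On that view this is a matter of labels. It stands to this extent: the test, alpha, power, sample size and boundaries for claiming non-inferiority are sound. It fails against the text, which says inferiority is to be concluded, and against the table, which lists it as a conclusion. Followed exactly, the plan produces the wrong statement.

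Four stronger readings are tempting, and the documents do not support them.

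- A reader might infer that the rule makes 65.49% of trials miss non-inferiority at +5 points. It does not. That figure is the complement of the disclosed 34.51%, and the 9.16% at equal rates is the planned type II error. Relabelling changes what those trials are called, not how many there are.
- A reader might infer that an inconclusive trial would be published as proof of harm. The plan sets a test conclusion. It contains no reporting rule to that effect and does not say that estimates will be withheld.
- A reader might infer that an interim stop would be equally uninformative. The look is already described as futility, a middle outcome (continue) exists, and a crossing needs an excess of about 16 points with a CI above 0. Early stops in the two truly non-inferior rows are 0.24% and 2.86%.
- A reader might infer that 'inferior' must be reserved for a CI wholly above 0.10. That is one convention among several, and at the final analysis it would be met in only about 1.0% of trials even at 25% v 35%.

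**Conclusion.** The point holds for the final rule. Section 12.3.2 treats failure to reject as acceptance of the null and leaves no outcome for a result that does not settle the question. On the plan's figures, inferiority is concluded in 9.16% of trials with identical arms and 65.49% with a true excess of 5 points, both inside the margin. How often this happens depends on the true difference. These figures assume a 25% control rate and are reproduced with 396 evaluable per arm. If the control rate were 50%, the power of about 80% stated in section 12.2 implies that about 20% of trials with identical arms would be concluded inferior.

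For the interim rule the point is narrower. The conclusion should match the stated futility purpose, because crossing -1.007 does not by itself establish an excess above 10 points.

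**What to change.** In section 12.3.2:

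- State that Z > 1.96 concludes non-inferiority and that Z at or below 1.96 means 'non-inferiority not demonstrated'.
- Add the two-sided 95% CI for Arm 2 minus Arm 1, and report where it lies relative to 0 and to 0.10.
- Base any statement of inferiority on that CI under a criterion fixed in advance. The team must choose it, because the options differ greatly. By simulation, a CI wholly above 0.10 at the final analysis occurs in under 0.01%, about 0.01% and about 1.0% of trials at 25% v 25%, 30% and 35%. A CI wholly above 0 with non-inferiority not shown occurs in 2.4%, 32.7% and 71.2%. A result of the second kind should be described as more complications, not as an excess beyond the margin.
- Relabel the final-analysis 'Inferior' column 'Non-inferiority not shown'.
- Describe Z < -1.007 at the interim as 'stopped for futility', and relabel that column and the accompanying text to match.

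The cost is a few sentences, the table headings and one added CI criterion. Sample size, alpha, power and both boundaries stay as they are.
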